9.3 POPULATIONS FOR ANALYSES

Intention-to-Treat (ITT) Analysis Dataset: All randomized patients analyzed according to their originally assigned treatment group, regardless of whether they actually received the assigned treatment, had treatment cross-over or protocol deviation, were lost to follow-up or partially withdrawn from the study.

As treated (AT) Analysis Dataset: All randomized patients analyzed according to the initial treatment actually received (TAVR or SAVR), irrespective of randomization assignment.

Safety Analysis Dataset: All randomized patients in whom the assigned valve-replacement procedure is initiated. Patients will be analyzed according to the procedure actually received.

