7 STUDY INTERVENTION DISCONTINUATION AND PATIENT DISCONTINUATION/WITHDRAWAL

7.1 FAILURE OF PATIENT TO UNDERGO RANDOMIZED TREATMENT ASSIGNMENT

Failure for a patient to undergo the randomized treatment assignment does not mean discontinuation from the study, and remaining study procedures should be completed as indicated by the study protocol. If a clinically significant finding is identified (including but not limited to changes from baseline) after randomization, the investigator or qualified designee will determine if any change in patient management is needed. Any new clinically relevant finding will be reported as an adverse event (AE).

The data to be collected pertaining to this eventuality will include the following: Documentation for reasons for deviation from randomized intervention (including cross over or decision for no intervention).

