7.2 PATIENT WITHDRAWAL FROM THE STUDY

Patients are free to withdraw from participation in the study at any time.

An investigator may discontinue or withdraw a patient from the study for the following reasons:

- Significant study intervention non-compliance
- If any clinical adverse event (AE), laboratory abnormality, or other medical condition or situation occurs such that continued participation in the study would not be in the best interest of the patient

The reason for patient discontinuation or withdrawal from the study will be recorded on the Case Report Form (CRF) specified in the MOP.

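### The Safety dataset leaves out patients who cross over before the assigned procedure starts and has no rule for conversions; sections 7.1 and 7.2 also need reconciling

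*Protocol*

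**What the plan says.** Protocol section 9.3 defines three datasets.

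- **ITT:** all randomized patients in their assigned group, "regardless of whether they actually received the assigned treatment, had treatment cross-over or protocol deviation, were lost to follow-up or partially withdrawn".
- **As-Treated:** "All randomized patients analyzed according to the initial treatment actually received (TAVR or SAVR), irrespective of randomization assignment".
- **Safety:** an entry condition followed by a grouping sentence, "All randomized patients in whom the assigned valve-replacement procedure is initiated. Patients will be analyzed according to the procedure actually received".

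Section 9.4.5 summarizes adverse events overall and by study arm. It does not say which dataset is used.

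On patients who do not get their allocation, section 7.1 states: "Failure for a patient to undergo the randomized treatment assignment does not mean discontinuation from the study". Section 7.2 states: "An investigator may discontinue or withdraw a patient from the study for the following reasons", and its first listed reason is "Significant study intervention non-compliance". The protocol does not define that term.

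**The concern.** The two sentences of the Safety definition work against each other. Grouping by procedure received is there to place patients whose treatment differed from their allocation. The entry condition has already removed most of them.

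The protocol expects such patients. Section 9.4.1 allows for a small number of crossovers, section 7.1 asks for the reason for any crossover, the trial is open-label (6.2), and up to two weeks may pass between randomization and the procedure (6.1.1). Adverse events are captured from randomization (8.10.5), so events in crossovers would be collected and then left out of any table built on the Safety dataset. Patients who switch procedure are unlikely to be a random sample, so this is a selective exclusion from a comparison with 13 listed safety endpoints (section 3).

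The few patients left for the grouping sentence are those whose assigned procedure was begun and who ended with the other one. These are among the most serious procedural failures, and the text does not say where they belong.

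Sections 7.1 and 7.2 raise a related question. If non-compliance includes not having the assigned procedure, an investigator could end study participation for patients whom section 7.1 intends to keep. Non-fatal and KCCQ outcomes could then be lost in an open-label trial.

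**Working it through.** **1. Apply each definition to each kind of patient**

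| Patient | ITT | As-Treated | Safety |
|---|---|---|---|
| Assigned procedure begun and completed | assigned arm | same | included, same |
| Crossed over before the assigned procedure began | assigned arm | procedure received | **excluded** |
| Assigned procedure begun, other valve implanted | assigned arm | by *initial* treatment received | included, **group not determined** |
| No procedure | assigned arm | no treatment to group by | excluded |

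Row 2 follows directly from the entry condition. Row 3 is the only one in which assigned and received treatment can differ inside the Safety dataset, so it is the only one in which the grouping sentence has work to do. That sentence lacks the word *initial* found in the As-Treated definition. For an abandoned TAVR followed by a surgical valve, SAVR received is a natural reading. For a deployed transcatheter valve followed by open surgery, TAVR received is equally tenable.

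**2. Number excluded.** The protocol gives no separate crossover rate. Its only figure is the 12.5% allowance in section 9.4.1, which covers crossover and loss to follow-up together: 0.125 × 1200 = 150 patients. Assuming a crossover proportion x, the number excluded is 1200x:

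- x = 1%: 12
- x = 3%: 36
- x = 5%: 60

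**3. Effect on a reported rate (illustration).** Suppose a full arm has event rate r = 10%, and crossovers carry k times that arm's average risk. Both values are assumptions. After exclusion the rate is (r − x·k·r)/(1 − x). With x = 5%:

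- k = 1: (0.10 − 0.005)/0.95 = 10.0%, no change
- k = 2: (0.10 − 0.010)/0.95 = 9.5%
- k = 3: (0.10 − 0.015)/0.95 = 8.9%

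**4. Conversions (illustration).** If a proportion c of 600 TAVR patients converts, and every one is read as SAVR received, 600c patients change group:

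- c = 0.5%: 3 patients, 3/603 = 0.5% of the SAVR group
- c = 1%: 6 patients, 6/606 = 1.0%
- c = 2%: 12 patients, 12/612 = 2.0%

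The TAVR group would show none of them. The values of c are assumptions, and the regrouping is one possible reading of the text.

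**5. Power.** The sample-size calculation (9.2, 9.4.1) does not use the Safety dataset. A simulation from Table 2 with 510 patients per arm gives 84.7% power against the stated 85.3%. That figure reproduces and is unaffected by this point.

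**6. Sections 7.1 and 7.2.** The intervention is a single valve procedure, and section 6.4 adds no other meaning of compliance. Not having the assigned procedure is therefore one plausible meaning of non-compliance. Section 4.3 counts a withdrawn patient as having completed participation. Section 7.4 keeps limited follow-up unless consent for all data collection is withdrawn, but the items it names are vital status, date of death and location of care. Stroke, reintervention, rehospitalization and KCCQ are not among them.

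**The case against.** The strongest defence is that *assigned* is loose drafting. The grouping sentence shows that the sponsor meant to keep crossovers, and both other datasets keep them. That may well be the intent, but the entry condition as written excludes them.

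Four stronger readings are tempting, and the protocol does not support them.

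- **A converted TAVR is counted as SAVR.** Section 9.3 has no conversion rule, so this is a possible effect of the wording, not something it states. The As-Treated wording is better but does not fully settle an abandoned TAVR either. Need for open heart surgery is also a poor example: section 3 defines it as a subsequent need following the index procedure, so a conversion during that procedure may not count in either group. A major cardiac structural complication, which includes injury needing unplanned intervention, is the clearer case.
- **Crossovers disappear from all safety tables.** Section 9.4.5 names no dataset, so this is not established. Death, stroke, reintervention and rehospitalization also belong to the primary hierarchy, and the ITT dataset retains crossovers.
- **Section 7.2 contradicts the ITT definition.** It does not. ITT keeps every randomized patient. Withdrawal can cost later data, but it does not remove the patient from the dataset.
- **Sections 7.1 and 7.2 flatly contradict each other.** That requires non-compliance to mean crossover, which the protocol does not say. Section 7.1 can be read as governing crossover. What remains is an unresolved tension.

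It is also fair to say that safety endpoints are listed as not powered, and that no direction of net bias has been shown.

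**Conclusion.** The point holds at moderate severity. On its literal wording the Safety dataset excludes patients who cross over before the assigned procedure begins. Its grouping sentence is then nearly empty, and the conversions it can still reach have no rule. This lies in text the protocol has already fixed, so it is not a detail left to the SAP.

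The size is uncertain because the protocol gives neither a crossover nor a conversion rate. Under an assumed 1% to 5% crossover, 12 to 60 of 1200 patients would be missing from analyses that use the Safety dataset. Any shift in a reported rate depends on how far crossovers differ in risk from other patients, which is unknown. The ITT and As-Treated datasets and all power figures are unaffected.

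Sections 7.1 and 7.2 are in tension over patients who do not receive the assigned procedure. The possible loss is in non-fatal and KCCQ outcomes, because section 7.4 protects vital status.

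**What to change.** - **Section 9.3:** define the Safety dataset as all randomized patients in whom any TAVR or SAVR procedure is initiated, grouped by the first procedure initiated. Conversions then stay with the procedure first attempted.
- **Section 9.4.5:** state that this dataset is used for the safety summaries, and make the description of the groups match it.
- **Sections 7.1 and 7.2:** reconcile the two passages, including what non-compliance with the intervention means, so that outcome collection continues for patients who do not receive the assigned procedure.

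The cost is a few sentences in a protocol amendment. No sample size, power calculation or data collection form needs to change.

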9.4 STATISTICAL ANALYSES

9.4.1 General Approach

Under the stated assumptions, we used 10,000 simulated trials to determine that 1020 patients with complete 3-year data achieves 85.3% power for a two-sided Finkelstein-Schoenfeld at a 5% significance level. Simulations randomly generated time-to-event data for each clinical event using an exponential distribution, with the rates for each component tailored so that the distribution of the most severe outcome within each patient followed the distribution given in Table 2. KCCQ outcomes were randomly generated from a binomial distribution. To allow for a small number of crossovers, loss-to-follow up (estimated at around an eighth or 12.5% of patients, in line with PARTNER trials), we propose to recruit a total of **1,200 randomized patients, 600 in each arm**. This sample size yields >95% power for the analysis of the key secondary outcome (a hierarchical composite of death and time-averaged KCCQ score) if SAVR improves the average KCCQ score by 3 points under the assumption that the standard deviation of an individual KCCQ measurement is 20. **Our key secondary outcome** is similar to the primary endpoint of the PCORI-funded RECHARGE study, which will study a hierarchical composite of death and SF-12 quality of life assessment, using the win ratio(5). Such a magnitude of improvement in KCCQ is regarded as clinically meaningful and, in context, is similar to that seen in novel heart failure drugs that have impacted survival and quality of life(6).

9.4.2 Analysis of The Primary Efficacy Endpoint(S)

The primary endpoint is a hierarchical composite of: (1) death within a shared follow-up period by a pair of patients, (2) disabling stroke within a shared follow-up period by a pair of patients, (3) non-disabling stroke within a shared follow-up period by a pair of patients, (4) valve reintervention within a shared follow-up period by a pair of patients, (5) rehospitalization (valve- or procedure-related, including heart failure, excluding valve reintervention within a shared follow-up period by a pair of patients; CEC adjudicated), and (6) unfavorable last available shared by a pair of patients KCCQ (VARC-3 definition: KCCQ <45 or decrease >10 points from baseline). This will be analyzed at latest available annual follow-up.

The primary analysis will use the unadjusted win ratio comparing all possible pairs of patients across treatment arms (one TAVR vs one SAVR), using the Finkelstein–Schoenfeld approach to prioritize more clinically important outcomes. For clinical event components, the pairwise comparison will consider both occurrence and timing of events, using all follow-up time within the PCORI-funded follow-up period that is common to both patients in the pair.

For the KCCQ component (lowest tier), the comparison will be based on whether the latest available KCCQ measurement for both patients (and occurring at least 1-year post-randomization) meets the unfavorable KCCQ definition. The win ratio will be reported with its 95% confidence interval, the p-value from the Finkelstein–Schoenfeld test, and a breakdown of wins/ties/losses at each hierarchical level.

As secondary analysis, the adjusted win ratio by stratification covariates will be performed. Adjustment method will be discussed in more details in the SAP.

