6.0 STUDY INTERVENTION

6.1 STUDY INTERVENTION(S) ADMINISTRATION

6.1.1 Study Intervention Description

The study intervention(s) (TAVR vs SAVR) are standard of care procedures performed with FDA-approved commercially available devices. Time between randomization and planned date of intervention should be 2 weeks or less.

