8.4 DISCHARGE or 7 DAYS POST-PROCEDURE (whichever is first)

The following assessments will be collected on the day of discharge (or 7 days post index procedure if the patient is not discharged by the 7th day). If the patient is discharged within 72 hours of index procedure, the post-procedure assessment should not be repeated.

- Physical Exam and vital signs
- Concomitant medications
- Adverse event assessment
- NIH Stroke Scale (NIHSS)
- Laboratory Test (Complete Blood Count and Comprehensive Metabolic Panel)
- 12-Lead ECG
- NYHA Classification
- QOR-15 scale (Quality of recovery)

8.5 30 DAY VISIT

The following assessments will be collected at 30 days (+ or – 7 days) from index-procedure.

- Physical Exam and vital signs
- Concomitant medications
- Adverse event assessment
- NIH Stroke Scale (NIHSS) and Modified Rankin Scale (mRS)
- Laboratory Test (Complete Blood Count, Comprehensive Metabolic Panel, and NT-proBNP)
- 12-Lead ECG
- Transthoracic Echocardiogram (TTE)
- NYHA Classification
- 6-Minute Walk Test
- Kansas City Cardiomyopathy Questionnaire (KCCQ)
- SF-12 Questionnaire
- QOR-15 scale (Quality of recovery)
- PHQ-9 scale (Depression score)

8.6 1 YEAR VISIT

The following assessments will be collected at 1 year (+ or – 30 days) from index-procedure.

- Physical Exam and vital signs
- Concomitant medications
- Adverse event assessment
- NIH Stroke Scale (NIHSS) and Modified Rankin Scale (mRS) (only for patients who develop a stroke post-index procedure)
- Laboratory Test (Complete Blood Count, Comprehensive Metabolic Panel, and NT-proBNP)
- 12-Lead ECG
- Transthoracic Echocardiogram (TTE)
- NYHA Classification
- 6-Minute Walk Test
- Kansas City Cardiomyopathy Questionnaire (KCCQ)
- SF-12 Questionnaire
- QOR-15 scale (Quality of recovery)
- PHQ-9 scale (Depression score)

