8.7 ANNUAL (2 to 10 YEAR) VISITS

The following assessments will be collected at 2 to 10 years (annually) (+ or – 45 days) from index-procedure.

- Physical Exam and vital signs
- Concomitant medications
- Adverse event assessment, including assessment of re-interventions or re-hospitalizations
- 12-Lead ECG (If available per standard of care)
- Transthoracic Echocardiogram (TTE)
- NYHA Classification
- Kansas City Cardiomyopathy Questionnaire (KCCQ)
- SF-12 Questionnaire
- PHQ-9 scale (Depression score)

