9.2 SAMPLE SIZE DETERMINATION

The study sample size has been calculated to achieve 85% power for the hierarchical composite outcome under the expected event rates given in Table 2 below. The expected SAVR event rate of 25.4% is based on 3-year SAVR rates from the PARTNER low risk study(3). This is a conservative approach since most patients will have more than 3 years follow-up and all patient data collected within the 6-year funded study period will be included. Comparisons in the win ratio are based on the most severe event experienced by each patient: we provide the assumed distribution of the most severe component of the primary outcome in the Table which is based on data from PARTNER-3. The assumed TAVR rates are then calculated assuming a relative risk of 0.75 comparing SAVR to TAVR.

Why we chose 25% surgical advantage (RR = 0.75) as a *reasonable estimate*:

- **Evidence spectrum:** randomized data (NOTION-2)(4) suggests a **~70 % benefit for surgery**, but this remains an inconclusive study given a very small sample size (n=100) designed for non-inferiority, but confidence intervals were very wide and spanned 1.0; the large Medicare dataset also suggesting survival advantage with SAVR though retrospective and claims-based. In addition, several administrative or meta-analytic datasets that show anywhere from **neutral to a small TAVR advantage**. Our assumption (25% benefit) sits **midway between clear surgical advantage to a possible slight TAVR edge**, acknowledging residual uncertainty.
- **Clinical plausibility:** Surgery, in removing the native leaflets, eliminates the impact of high TAVR risk anatomy (excessive valve and raphe calcium) yet TAVR, with less invasiveness offers significant putative advantages, reflected in early follow up data from the TAVR vs SAVR trials in tricuspid aortic valve. A **25% composite difference** balances these competing effects.
- **Bottom line:** Published 1-year results range widely from strong surgical benefit to slight TAVR benefit depending on data source and methodology. All involve predominantly older, higher-risk patients. Thus, in the presence of enormous uncertainty, using RR = 0.75 represents a *conservative midpoint* that:
 - Reflects the full observed range,
 - Incorporates known anatomic/mechanical advantages of SAVR in BAV, and
 - Preserves statistical power without over-promising effect size.

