9.4.8 Handling of missing data

The extent and pattern of missing data will be summarized by study arm and visit, including reasons for missingness when available.

For the Winratio analysis, participants without KCCQ at least 1-year post-randomization will have their KCCQ comparison considered as non-evaluable/tier, unless a higher-level component has already determined the winner.

For time-to-event endpoints, participants without an event will be right-censored at the last known contact date.

For longitudinal patient-reported and functional outcomes, models fitted by full maximum likelihood will be used, which provide valid inference under a missing-at-random (MAR) assumption conditional on included covariates and observed outcomes. As sensitivity analyses, departures from the MAR assumption will be assessed using delta-adjusted pattern-mixture models. Following multiple imputation under MAR, imputed outcome values occurring after permanent dropout will be systematically shifted by clinically meaningful offsets (δ) to reflect plausible worse (or better) unobserved outcomes. A range of δ values will be examined to evaluate robustness of conclusions.

For time-averaged KCCQ, missing KCCQ measurements will be imputed based on the the mean estimates from a linear mixed model with time as categorical covariate, study arm and the interaction between study arm and time as fixed effects and subject-specific random effects.

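### The calendar cut on KCCQ in tier 6 of the primary endpoint conflicts with the early half of the 1-year visit window, and the pairing rule is worded in two ways (minor; costless to fix)

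*Protocol*

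**What the plan says.** - **Eligibility rule, Protocol Section 9.4.2.** The KCCQ tier compares patients on "the latest available KCCQ measurement for both patients (and occurring at least 1-year post-randomization").
- **Consequence, Section 9.4.8.** In the win ratio analysis, "participants without KCCQ at least 1-year post-randomization will have their KCCQ comparison considered as non-evaluable/tier" (the last word is evidently meant as a tie), unless a higher tier has already decided the pair.
- **Visit timing, Section 8.6.** The 1-year assessments, KCCQ among them, "will be collected at 1 year (+ or – 30 days) from index-procedure". The Schedule of Activities gives the same window. Section 8.7 sets the later visits: "The following assessments will be collected at 2 to 10 years (annually) (+ or – 45 days) from index-procedure".
- **Delay to procedure, Section 6.1.1.** "Time between randomization and planned date of intervention should be 2 weeks or less".
- **Pairing.** The endpoint definition that opens Section 9.4.2 describes tier 6 as "unfavorable last available shared by a pair of patients KCCQ". The paragraph on the KCCQ component uses the eligibility wording above instead.
- **Stated timepoint.** Table 1 and Section 9.4.2 both say that the primary endpoint is assessed at the latest annual follow-up available.

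**The concern.** The cut is a day count from randomization. The visit is a window around the procedure anniversary. The two do not line up: a visit made on schedule, in the early part of its window, yields a KCCQ that the analysis rule refuses. If the patient has no later score, or the pair shares no later one, that tier-6 comparison becomes a tie although both scores were collected as planned.

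The pairing has a separate ambiguity. A rule based on the last visit the two patients share compares them at the same point in follow-up. A rule based on each patient's own latest score could set a year-1 status against a year-6 status. This belongs to the definition of the primary endpoint of an open-label trial, so it should have one reading before outcome data accumulate.

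**Working it through.** **1. The plan's own power.** Inputs: Table 2 distributions (composite 25.4% SAVR, 34.1% TAVR), 510 patients per arm, complete 3-year data, and a two-sided 5% Finkelstein–Schoenfeld test (Sections 9.2 and 9.4.1). Clinical tiers were simulated as exponential times and KCCQ as binomial, with 10,000 trials per scenario. Result: 84.6%, against the stated 85.3%. The plan's figure is reproduced.

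**2. Where a compliant visit can fall.** With the procedure *D* days after randomization, the window runs from day 335 + *D* to day 395 + *D*. It opens on day 335 if *D* = 0 and on day 349 if *D* = 14. Both precede day 365.

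**3. Share of in-window 1-year visits before the cut.** Assuming visits uniform over ±30 days, the share is (30 − *D*)/60:

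| Delay *D* | Share before day 365 |
|---|---|
| 0 days | 30/60 = 50% |
| 7 days (also the average for *D* uniform on 0 to 14) | 23/60 = 38% |
| 14 days | 16/60 = 27% |

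If visits cluster normally around the anniversary with SD 15 days, the share is 33%.

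**4. When that costs a comparison.** The score is needed only if nothing later is usable. Assumptions: analysis cut at 6 years, uniform accrual, and the 12.5% allowance of Section 9.4.1 treated as exponential loss by 3 years.

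With accrual of up to 4 years, nearly everyone could reach year 2, so only loss to follow-up leaves year 1 as the last visit.

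- Patients with a 1-year visit and nothing later: 1 − 0.875^(1/3) = 4.4%. Made non-evaluable: 4.4% × 0.383 = 1.7%.
- Pairs whose last shared visit is year 1: 1 − 0.875^(2/3) = 8.5%. Such a pair fails if either score is early: 1 − (37/60)² = 62%. Voided: 8.5% × 0.62 = 5.3%.
- If each patient's own latest score is used: 1 − (1 − 0.017)² = 3.3% voided.

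Under the shared-visit reading, 4.5 years of accrual gives 28% of pairs with year 1 as last shared visit and 17% voided; 5 years gives 41% and 26%.

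**5. Effect on power**, with non-evaluable patients chosen independently of arm and outcome:

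| Patients non-evaluable at tier 6 | Power |
|---|---|
| 0% | 84.6% |
| 2% | 84.3% |
| 5% | 84.3% |
| 10% | 83.5% |
| 20% | 81.4% |
| No KCCQ tier at all | 73.1% |

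Simulation error is about ±0.7 points. Voiding 5.3% of pairs corresponds to about 2.7% of patients (1 − 0.973² = 5.3%), between the 2% and 5% rows.

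**6. Pairing.** On the assumptions of step 4, with accrual of 3 to 5 years, the two patients' last annual visits differ in 72% to 80% of evaluable pairs, and by two or more years in 31% to 48%. The reading chosen therefore determines which scores are compared in most pairs that reach tier 6.

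**The case against.** **The intent is visible.** Post-baseline KCCQ is scheduled only at 30 days, 1 year and annually, and the endpoint is stated to be assessed at the latest annual follow-up. On that reading the 1-year cut merely excludes the 30-day score, and mapping visits to windows is commonly left to the SAP. This is a fair account of what was probably meant. But the protocol states an operative rule in one section and its consequence in another, and following the text discards compliant data. That is a conflict, not an omitted detail.

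**The pairing phrases may be one rule**, namely the latest measurement both patients have, especially since the clinical tiers are confined to common follow-up. This is plausible, but the second phrase can equally be read as each patient's own latest score.

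**Few of the voided comparisons would have been decided.** From Table 2, unfavorable KCCQ among patients reaching tier 6 is 5.0/79.6 = 6.3% (SAVR) and 6.7/72.6 = 9.2% (TAVR). About 86% of such pairs tie anyway. This stands, and explains the small power effect.

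Stronger inferences that the documents do not support:

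- *That counting visits from the procedure causes the loss.* The procedure follows randomization, so this anchor moves visits later and offsets up to 14 days. The cause is the early side of the window.
- *That 38% of 1-year scores drop out of the primary endpoint.* Where a later score is usable, the latest-score rule supersedes the early one in any case, and Section 9.2 expects that "most patients will have more than 3 years follow-up".
- *That a quarter of tier-6 comparisons are lost.* This needs about 5 years of accrual, which the protocol does not state. With a 6-year cut, only 3/5 × 1200 = 720 patients could then reach 3 years, against the 1020 with complete 3-year data in Section 9.4.1. Four years gives 900, so this check does not fix the accrual period, but it does count against the longest scenarios.
- *That the arms are affected differently.* No delay by arm is given, the planned limit is common to both, and no bias has been shown.

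**Conclusion.** The inconsistency is real and minor. Taken literally, Sections 9.4.2 and 9.4.8 reject a protocol-compliant 1-year KCCQ dated before day 365 whenever no later usable score exists for the patient or pair. About 38% of in-window 1-year visits are exposed (27% to 50% by delay). About 5% of tier-6 comparisons would be voided with 3 to 4 years of accrual, and more if accrual is longer. Power falls by about 0 to 1 point with up to 10% of patients non-evaluable.

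These sizes rest on uniform visit timing, a 0 to 14 day delay, the 12.5% allowance taken as loss by 3 years, an assumed accrual period, and non-evaluability unrelated to arm or outcome. The existence of the conflict rests on none of them. The two pairing phrases are an ambiguity rather than a proven contradiction. The reason to act is that the primary endpoint should have one definition, not that power is at risk.

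**What to change.** In Section 9.4.2, replace the calendar cut and both pairing phrases with one rule: tier 6 uses the KCCQ at the latest nominal annual visit (12-month visit or later, within its protocol window) completed by both patients of the pair. In Section 9.4.8, make the comparison non-evaluable only when the pair has no such visit, and correct the apparent misprint of tie. State that visits are counted from randomization for patients who have no procedure: Sections 7.1 and 9.3 keep them in follow-up and in the intention-to-treat set, but the visit windows give them no anchor.

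Cost: about one sentence in each of the two sections. There are no new data, no change to the visit schedule and no effect on sample size.
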